6.8.2. Historical Illnesses and Preexisting Conditions

Historical illnesses and preexisting conditions will be classified using the latest version of the Medical Dictionary for Regulatory Activities (MedDRA).

Historical illness/condition is defined as the condition/event recorded on the Pre-Existing Conditions and Medical History eCRF page or on the Prespecified Medical History eCRF page with an end date prior to the date of informed consent.

A preexisting condition is defined as the condition/event recorded on the Pre-Existing Conditions and Medical History eCRF page or on the Prespecified Medical History eCRF page with a start date prior to the date of informed consent, and no end date (that is, the event is ongoing) or an end date on or after the date of informed consent. Adverse events occurring prior to the date of first study injection will also be reported. Note that, if a preexisting condition worsens in severity on or after the date of informed consent, it will be recorded as an AE on Adverse Events eCRF page from the date of worsening onward.

The following summaries will be provided for both ITT Populations:

- The number and percentage of patients with historical illnesses by treatment group and overall, by System Organ Class (SOC) and preferred term (PT).
- The number and percentage of patients with preexisting conditions and adverse events occurring prior to the first dose, by treatment group and overall, by SOC and PT.
- The number and percentage of patients with prespecified medical history (hypertension; diabetes mellitus, Type I; diabetes mellitus, Type II; dyslipidemia; psoriatic arthritis;

inflammatory bowel disease [Crohn's disease and uncreative colitis]), by treatment group and overall.

For a condition/event that is gender-specific (as defined by MedDRA), the denominator and computation of the percentage will include only patients from the given gender.

The comparisons among treatment groups will be conducted using Fisher's exact test.

By-patient listings of historical illnesses and preexisting conditions, respectively, for the ITT Populations will be provided.

6.9. Treatment Compliance

By-patient listings of randomization schedules and study drug dispensed (include the clinical trial (CT) Lot number), respectively, for the ITT Populations will be provided.

Throughout treatment periods, randomized patients will record information in a Study Drug Administration Log (captured in the Exposure as Collected eCRF page), including the date, time, and anatomical location of administration of investigational product, syringe number, who administered the investigational product, and the reason if the investigational product was not fully administered.

Treatment compliance for each patient per period will be calculated as:

$$\text{Treatment compliance (\%)} = 100 \times \frac{\text{Total number of injections administered}}{\text{Total number of injections prescribed}}$$

Clinical Protocol RHCD:

- For patients who complete Period 2 and receive ixekizumab 20 mg or 40 mg or placebo for ixekizumab 20 mg or 40 mg, the number of injections prescribed (that is, expected) during Period 2 will be equal to 3 (1 injection at Week 0 and 1 injection at Weeks 4 and 8).
For patients who complete Period 2 and receive ixekizumab 80 mg or placebo for ixekizumab 80 mg, the number or injections prescribed during Period 2 will be equal to 4 (2 injections at Week 0 and 1 injection at Weeks 4 and 8).
- For patients who discontinue during Period 2, the number of injections prescribed during Period 2 can be derived from the IWRS study drug dispense dataset.

Protocol Addendum RHCD(2):

- The number of injections for ixekizumab group and placebo group are the same as in the main study ITT Population. For patients who complete Period 2 and receive etanercept, the number of injections prescribed during period 2 will be equal to 12 (1 injection every week from Week 0 to Week 11).
- For patients who discontinue during Period 2, the number of injections prescribed during Period 2 can be derived from the IWRS study drug dispense dataset.

A patient will be considered overall compliant with study treatment within each treatment period if he/she misses no more than 20% of the expected doses, does not miss 2 consecutive doses, and

does not overdose (that is, take more injections at the same time point than specified in the protocol).

Patient treatment compliance, by Period 2, will be summarized. The comparisons between treatment groups during Period 2 will be conducted using Fisher's exact test.

A by-patient listing of study treatment administration and compliance for the ITT Population will be provided.

6.10. Previous and Concomitant Therapy

Medication/therapy will be classified into Anatomical Therapeutic Chemical (ATC) drug classes using the latest version of the World Health Organization (WHO) Drug Dictionary.

A by-patient listing of previous and concomitant therapy, and a by-patient listing of previous Ps therapy for the ITT Population will be provided.

6.10.1. Previous Therapy

Previous therapy is defined as therapy that starts and ends prior to the date of first dose of study treatment in the Double-Blind Treatment Period (Period 2). If therapy start and/or end dates are missing or partial, the dates will be compared as far as possible with the date of first dose of study treatment in Period 2. If there is clear evidence to suggest that the therapy stopped prior to the first dose of study treatment in Period 2, the therapy will be assumed to be previous dose only. The comparisons will be conducted using Fisher's exact test.

The following summaries will be provided for both ITT populations:

- Previous therapy (captured in the Prior Therapy: Psoriasis eCRF page and Concomitant Therapy eCRF page) by WHO ATC Level 4 and WHO PT.
- Previous Ps therapy captured in the Prior Therapy: Psoriasis eCRF page to be summarized according to type (topical prescription therapy, topical nonprescription therapy, nonbiologic systemic agent, biologic agent, nonbiologic nonsystemic agent, phototherapy) and therapy. The previous biologic agent will be further classified as tumor necrosis factor- (TNF-) α inhibitor (includes infliximab, etanercept, adalimumab, golimumab, certolizumab pegol), interleukin- (IL-) 12/23 inhibitor (includes ustekinumab), IL-17 inhibitor (includes secukinumab and brodalumab), and other (includes efalizumab, alefacept, or other biological agents).
- The number and percentage of patients with each reason for discontinuation of previous Ps therapy to be summarized by type and therapy.

6.10.2. Concomitant Therapy

Concomitant therapy is defined as the therapy that starts before, on, or after the first day of study treatment in the defined treatment period and before the last visit date in the treatment period, and continues into the treatment period, that is, either no end date (the therapy is ongoing) or an end date on or after the first day of study treatment in treatment period. Note, concomitant

therapy will belong to a treatment period if the therapy starts and ends on the exact same day as the first day of study treatment of the treatment period.

Concomitant therapy during period 2 will be summarized by both ITT populations. Concomitant therapy for Period 2 is defined as the therapy that starts before, on, or after the first day of study treatment of Period 2 and before the last visit date of Period 2, and continues into Period 2, that is, there is either no end date (the therapy is ongoing) or there is an end date on or after the first day of study treatment of Period 2. Note that concomitant therapy will belong to Period 2 if the therapy starts and ends on the exact same day as the first day of study treatment of Period 2.

Concomitant therapy during period 4 will be summarized by the Double-Blind Randomized Withdrawal Period Population. Concomitant therapy for Period 4 is defined as the therapy that starts before, on, or after the first day of study treatment of Period 4 and before the last visit date of Period 4, and continues into Period 4, that is, there is either no end date (the therapy is ongoing) or there is an end date on or after the first day of study treatment of Period 4. Note that concomitant therapy will belong to Period 4 if the therapy starts and ends on the exact same day as the first day of study treatment of Period 4.

The comparisons will be conducted using Fisher's exact test.

The following summaries will be provided:

- Concomitant therapy by WHO ATC Level 4 and WHO PT
- The number and percentage of patients taking concomitant therapy of a topical product to be summarized for topical and topical steroid therapies, respectively, by WHO ATC Level 4 and WHO PT. The definition of concomitant topical therapy can be found in [Appendix 1](#). Please refer to IIF-MC-RHCD Clinical Protocol Section 7.7 for concomitant therapies permitted during the study.
- The number and percentage of patients who received premedication for allergic reaction/hypersensitivity captured in the Allergic/Hypersensitivity Reaction Follow-Up eCRF page.

If a partial or completely missing medication start date/time or end date/time is present, the following imputation rules will be utilized in the analysis:

- For the start date:
 - If year, month, and day are missing, then use the earlier of the patient's first visit date or the consent date.
 - If either month or month and day are missing, then use January 1.
 - If only day is missing, impute the first day of the month.
- For the start time:
 - Impute as 23:59
- For the end date:
 - If year, month, and day are missing, then use the patient's last visit date.
 - If either month or month and day are missing, then use December 31.
 - If only day is missing, then use the last day of the month.

- The imputed date will not be beyond the patient's last visit date.
- For the end time:
 - Impute as 23:59.
- If there is any doubt, the medication will be flagged as concomitant.

6.11. Efficacy Analyses

Table RHCD.6.3 includes the description and derivation of the primary and secondary efficacy outcomes. Table RHCD.6.4 includes the description of primary and secondary efficacy analyses.

Table RHCD.6.3. Description and Derivation of Primary and Secondary Efficacy Outcomes

Measure	Description	Variable	Derivation / Comment	Imputation Approach if with Missing Components
PASI	
Psoriasis Area and Severity Index (PASI): combines assessments of the extent of body-surface involvement in 4 anatomical regions (head and neck, trunk, arms, and legs) and the severity of scaling (S), redness (R), and plaque induration/infiltration (thickness, T) in each region, yielding an overall score of 0 for no psoriasis to 72 for the most severe disease (Fredriksson and Pettersson 1978). Severity is rated for each index (R, S, T) on a 0-4 scale (0 for no involvement up to 4 for severe involvement):
 
0 = none 1 = slight 2 = mild 3 = moderate 4 = severe
 
The body is divided into four anatomical regions comprising the head (h), upper limb (u), trunk (t), and lower limb (l). In each of these areas, the fraction of total body surface area affected is graded on a 0-6 scale (0 for no involvement up to 6 for 90% - 100% involvement):
 
0 = 0% (clear) 1 = >0% to <10% 2 = 10% to <30% 3 = 30% to <50% 4 = 50% to <70% 5 = 70% to <90% 6 = 90% to 100%
 
The various body regions are weighted to
	PASI score	
The composite PASI score is calculated by multiplying the sum of the individual-severity scores for each area by the weighted area-of-involvement score for that respective area, and then summing the 4 resulting quantities as follows: $PASI = 0.1(Rh + Th + Sh)Ah + 0.2(Ru + Tu + Su)Au + 0.3(Rt + Tt + St)At + 0.4(Rl + Tl + Sl)Al$, where: Rh, Ru, Rt, Rl = redness score of plaques on the head, upper limb, trunk, and lower limb, scored 0-4 respectively; Th, Tu, Tt, Tl = thickness score of plaques on the head, upper limb, trunk, and lower limb, scored 0-4 respectively; Sh, Su, St, Sl = scaliness score of plaques on the head, upper limb, trunk, and lower limb, scored 0-4 respectively; Ah, Au, At, Al = numerical value translation of % area of psoriatic involvement score for the head, upper limb, trunk, and lower limb, respectively. PASI scores are treated as a continuous score, with 0.1 increments within these values.
	If any individual score is missing, the PASI score will not be calculated, hence, missing.
		PASI change from baseline	Calculated as: observed PASI – baseline PASI	Missing if baseline or observed value is missing.
		PASI percent improvement from baseline	
Calculated as:
 $Percent\ improvement\ from\ baseline = 100 \times \frac{Baseline\ PASI - Observed\ PASI}{Baseline\ PASI}$ 
If a patient has experienced an improvement, this measure will be positive. If a patient has experienced a worsening in the condition, this measure will be
	Missing is baseline or observed value is missing

Measure	Description	Variable	Derivation / Comment	Imputation Approach if with Missing Components
	reflect their respective proportions of body surface area (BSA).		negative.	
		PASI 75 (co-primary)	A clinically meaningful response; at least a 75% improvement in PASI score from baseline.	Missing is baseline or observed value is missing
		PASI 90	Higher level of clearance; at least a 90% improvement in PASI score from baseline.	Missing is baseline or observed value is missing
		PASI 100	Complete resolution of plaque psoriasis; a 100% improvement in PASI score from baseline.	Missing is baseline or observed value is missing
sPGA	Static Physician Global Assessment (sPGA): the physician’s global assessment of the patient’s psoriasis lesions at a given time point (EMA 2004 [WWW]). Plaques are assessed for induration, erythema, and scaling, and an overall rating of psoriasis severity is given using the anchors of clear (0), minimal (1), mild (2), moderate (3), severe (4), or very severe (5).	sPGA score	Range from 0 to 5: clear (0); minimal (1); mild (2); moderate (3); severe (4); or very severe (5).	Single item, missing if missing
		sPGA (0,1) (co-primary)	An sPGA assessed as either 0 or 1, which represents a clinically meaningful response of minimal plaque severity or complete resolution of plaque psoriasis.	Missing if sPGA is missing
		sPGA (0)	An sPGA assessed as 0, which represents a clinically important endpoint indicating complete resolution of plaque psoriasis.	Missing if sPGA is missing
BSA	Percentage of BSA: The investigator will evaluate the percentage involvement of psoriasis on each patient’s BSA on a continuous scale from 0% (no involvement) to 100% (full involvement), in which 1% corresponds to the size of the patient’s hand (including the palm, fingers, and thumb) (Van Voorhees et al. 2009).	BSA	Collected as a single scale as part of PASI electronic case report form (eCRF) page. Range from 0% to 100%.	Missing is baseline or observed value is missing
		BSA change from baseline	Calculated as: observed BSA – baseline BSA	Missing is baseline or observed value is missing

Measure	Description	Variable	Derivation / Comment	Imputation Approach if with Missing Components
NAPSI	
Nail Psoriasis Severity Index (NAPSI): will be used if the patient has nail psoriasis at baseline. The NAPSI is a numeric, reproducible, objective tool for evaluation of nail psoriasis. This scale is used to evaluate the severity of nail bed psoriasis and nail matrix psoriasis by area of involvement in the nail unit. In this study, both fingernail and toenail involvement will be assessed. The nail is divided with imaginary horizontal and longitudinal lines into quadrants. Each nail is given a score for nail bed psoriasis (0 to 4) and nail matrix psoriasis (0 to 4), depending on the presence (score of 1) or absence (score of 0) of any of the features of nail bed and nail matrix psoriasis in each quadrant:
 
0 = None 1 = present in one quadrant of nail 2 = present in two quadrants of nail 3 = present in three quadrants of nail 4 = present in four quadrants of nail
	NAPSI score	The NAPSI score of a nail is the sum of scores in nail bed and nail matrix from each quadrant (maximum of 8). Each nail is evaluated, and the sum of all the fingernails and toenails is the total NAPSI score (range, 0 to 160), usually indicated as NAPSI score.	For each nail, if either bed or matrix score is missing or not done, the score for that nail is missing. If <50% of the nail scores from 20 nails are missing, the imputation will be performed by using the average score of the remaining nails. If ≥50% of the nail scores are missing, the NAPSI score will be left as missing.
		NAPSI score change from baseline	Calculated as: observed NAPSI – baseline NAPSI	Missing if baseline or observed value is missing
		NAPSI score = 0	A NAPSI response is defined as a NAPSI score of 0, which is also referred to as nail clearance.	Missing if NAPSI score is missing.
PSSI*	
Psoriasis Scalp Severity Index (PSSI): will be used if the patient has scalp psoriasis at baseline. The scalp will be assessed for erythema (redness), induration (hardness), and desquamation (shedding of skin) and percentage of area affected as follows: Erythema, Induration and Desquamation: 0 = Absent
	PSSI score	The PSSI score is a composite score derived from the sum of the scores for erythema, induration and desquamation multiplied by the score for the extent of scalp area involved (percent of scalp involved). The range is 0 to 72.	If any individual score is missing, the PSSI score will not be calculated, hence, missing.

Measure	Description	Variable	Derivation / Comment	Imputation Approach if with Missing Components
	1 = Slight 2 = Moderate 3 = Severe 4 = Severest Possible Percent of Scalp Involved: 1 = <10% 2 = 10% – 29% 3 = 30% – 49% 4 = 50% – 69% 5 = 70% – 89% 6 = 90% – 100%	PSSI score change from baseline	Calculated as: observed PSSI – baseline PSSI	Missing if baseline or observed value is missing
		PSSI score = 0	A PSSI response is defined as a PSSI score of 0, which is also referred to as scalp clearance.	Missing if PSSI score is missing.
PPASI	Palmoplantar Psoriasis Area and Severity Index (PPASI): will be used if the patient has palmoplantar psoriasis at baseline. Both the palms and soles on each hand and foot will be individually assessed for erythema, induration, desquamation and percentage of area affected as follows: Erythema (E), Induration (I), and Desquamation (D): 0 = None 1 = Slight 2 = Moderate 3 = Severe 4 = Very Severe Percent of Palm and Sole Area Covered: 0 = None 1 = <10% 2 = 10% – 29% 3 = 30% – 49% 4 = 50% – 69% 5 = 70% – 89%	PPASI score	The PPASI score is a composite score derived from the sum scores for erythema, induration, and desquamation multiplied by a score for the extent of palm and sole area involvement. The range is 0 to 72. $PPASI = 0.2(Erp + Irp + Drp)Arp + 0.2(Elp + Ilp + Dlp)Alp + 0.3(Ers + Irs + Drs)Ars + 0.3(ElS + IlS + DlS)AlS$, where: Erp, Elp, Ers, ElS = Erythema score of plaques on the right palm (rp), left palm (lp), right sole (rs), left sole (lS), scored 0-4 respectively; Irp, Ilp, Irs, IlS = Induration score of plaques on the right palm (rp), left palm (lp), right sole (rs), left sole (lS), scored 0-4 respectively; Drp, Dlp, Drs, DlS = Desquamation score of plaques on the right palm (rp), left palm (lp), right sole (rs), left sole (lS), scored 0-4 respectively; Arp, Alp, Ars, AlS = numerical value translation of % area covered for the right palm, left palm, right sole, and left sole, respectively.	If any individual score is missing, the PPASI score will not be calculated, hence, missing.
		PPASI change	Calculated as: observed PPASI – baseline PPASI	Missing if baseline or

Measure	Description	Variable	Derivation / Comment	Imputation Approach if with Missing Components
	6 = 90% – 100%	from baseline		observed value is missing
		PPASI percent improvement from baseline	Calculated as: $\text{Percent improvement from baseline} = 100 \times \frac{\text{Baseline PPASI} - \text{Observed PPASI}}{\text{Baseline PPASI}}$ If a patient has experienced an improvement, this measure will be positive. If a patient has experienced a worsening in the condition, this measure will be negative.	Missing is baseline or observed value is missing
		PPASI 50	At least a 50% improvement in PPASI score from baseline.	Missing is baseline or observed value is missing
		PPASI 75	At least a 75% improvement in PPASI score from baseline.	Missing is baseline or observed value is missing
		PPASI 100	A 100% improvement in PPASI score from baseline.	Missing is baseline or observed value is missing
Binary questions on psoriasis location	The presence of visible psoriasis on the following locations will be noted: 1. Face 2. Nail 3. Axilla 4. Genitals 5. Perianal region	Binary questions on psoriasis location	Binary responses (yes/no) will be noted to determine the presence of visible psoriasis on each of the 5 locations.	Missing if the response is missing

* A previous version of PSSI questionnaire was sent to the sites with percent of scalp involved range 1 to 6. Some sites still enter 0 to represent none scalp psoriasis involvement. The range of the total score is still 0 – 72, so that there is no impact on planned analyses.

Table RHCD.6.4. Description of Primary and Secondary Efficacy Analyses

Measure	Variable	Analysis (Method)	Population	Comparison/Time Point	Analysis Type
PASI	PASI 75 (co-primary)	Fisher’s exact test with NRI (primary analysis) Logistic regression with NRI	ITT Population	Ixekizumab Q4W vs. placebo at Week 12 and all other postbaseline visits during Period 2.	Primary analysis is Fisher’s exact test with NRI for ITT Population comparing ixekizumab and placebo at Week 12. Secondary analysis is logistic regression with NRI for ITT Population comparing ixekizumab and placebo at Week 12.
		Fisher’s exact test with NRI Logistic regression with NRI	Per-Protocol Set	Ixekizumab Q4W vs. placebo at Week 12 and all other postbaseline visits during Period 2.	Additional analysis for co-primary outcomes.
	PASI 75	Fisher’s exact test with NRI Logistic regression with NRI	ITT Population	Ixekizumab Q4W vs. placebo at Week 4.	Gated secondary analysis
			ITT Population - Etanercept-approved countries	All pairwise comparisons at Week 12 and all other postbaseline visits during Period 2.	Other secondary analysis
	PASI 90	Fisher’s exact test with NRI Logistic regression with NRI	ITT Population	Ixekizumab Q4W vs. placebo at Week 12 and all other postbaseline visits during Period 2.	Gated secondary analysis comparing ixekizumab Q4W vs. Placebo at Week 12.
	PASI 100	Fisher’s exact test with NRI Logistic regression with NRI	ITT Population	Ixekizumab Q4W vs. placebo at Week 12 and all other postbaseline visits during Period 2.	Gated secondary analysis comparing ixekizumab Q4W vs. Placebo at Week 12.
PASI 50	Fisher’s exact test with NRI Logistic regression with NRI	ITT Population	Ixekizumab Q4W vs. placebo at Week 12 and all other postbaseline visits during Period 2.	Other secondary analysis	

Measure	Variable	Analysis (Method)	Population	Comparison/Time Point	Analysis Type
	Change from baseline, percent improvement	ANCOVA with LOCF; MMRM	ITT Population	Ixekizumab Q4W vs. placebo at Week 12 and all other postbaseline visits during Period 2.	Other secondary analysis
	PASI 75 PASI 90 PASI 100	Summarize	Ixekizumab Efficacy Primary Population	At all postbaseline visits during the Combined Treatment Periods (Periods 2, 3, and 4).	Other secondary analysis/ Exploratory analysis
			Ixekizumab Efficacy Secondary Population	At all postbaseline visits during the Combined Treatment Periods (Periods 3 and 4).	Exploratory analysis
		Fisher's exact test	Double-Blind, Randomized Withdrawal Population	Ixekizumab Q4W vs. placebo at all postbaseline visits during Period 4.	Other secondary analysis
sPGA	sPGA (0,1) (co-primary)	Fisher's exact test with NRI (primary analysis); Logistic regression with NRI	ITT Population	Ixekizumab Q4W vs. placebo at Week 12 and all other postbaseline visits during Period 2.	Primary analysis is Fisher's exact test with NRI for ITT Population comparing ixekizumab and placebo at Week 12. Secondary analysis is logistic regression with NRI for ITT Population comparing ixekizumab and placebo at Week 12.
		Fisher's exact test with NRI Logistic regression with NRI	Per-Protocol Set	Ixekizumab Q4W vs. placebo at Week 12 and all other postbaseline visits during Period 2.	Additional analysis for co-primary outcomes.
	sPGA (0,1)	Fisher's exact test with NRI Logistic regression with NRI	ITT Population	Ixekizumab Q4W vs. placebo at Week 4.	Gated secondary analysis
			ITT Population - Etanercept approved	Ixekizumab Q4W vs. etanercept at Week 12 and all	Other secondary analysis

Measure	Variable	Analysis (Method)	Population	Comparison/Time Point	Analysis Type
			countries	other postbaseline visits during Period 2.	
			Double-Blind, Randomized Withdrawal Period Population	Ixekizumab Q4W vs. placebo at Week 108 and all other postbaseline visits during Period 4.	Other secondary analysis
	sPGA (0)	Fisher’s exact test with NRI Logistic regression with NRI	ITT Population	Ixekizumab Q4W vs. placebo at Week 12 and all other postbaseline visits during Period 2.	Gated secondary analysis
	sPGA (0,1) sPGA (0)	Fisher’s exact test with NRI Logistic regression with NRI	ITT Population	Ixekizumab Q4W vs. placebo at Week 12 and all other postbaseline visits during Period 2.	Other secondary analysis
	sPGA (0,1) sPGA (0)	Summarize	Ixekizumab Efficacy Primary Population	At all postbaseline visits during the Combined Treatment Periods (Periods 2, 3, and 4).	Other secondary analysis/ Exploratory analysis
			Ixekizumab Efficacy Secondary Population	At all postbaseline visits during the Combined Treatment Periods (Periods 3 and 4)	Exploratory analysis
	Time to relapse to sPGA ≥ 2	Log-rank test Kaplan-Meier estimate	Double-Blind, Randomized Withdrawal Period Population	Ixekizumab Q4W vs. placebo during the Double-Blind Randomized Withdrawal Period.	Other secondary analysis
BSA	Change from baseline	ANCOVA with LOCF; MMRM	ITT Population	Ixekizumab Q4W vs. placebo at Week 12 and all other postbaseline visits during Period 2.	Other secondary analysis

Measure	Variable	Analysis (Method)	Population	Comparison/Time Point	Analysis Type
NAPSI	Change from baseline	ANCOVA with LOCF MMRM	ITT Population – patients with baseline nail involvement (NAPSI baseline score >0)	Ixekizumab Q4W vs. placebo at Week 12 and all other postbaseline visits during Period 2.	Other secondary analysis
	NAPSI score = 0	Fisher exact test with NRI Logistic regression with NRI	ITT Population – patients with baseline nail involvement (NAPSI baseline score >0)	Ixekizumab Q4W vs. placebo at Week 12 and all other postbaseline visits during Period 2.	Exploratory analysis
PSSI	Change from baseline	ANCOVA with LOCF; MMRM	ITT Population – patients with baseline scalp involvement (PSSI baseline score >0)	Ixekizumab Q4W vs. placebo at Week 12 and all other postbaseline visits during Period 2.	Other secondary analysis
	PSSI score = 0	Fisher’s exact test with NRI Logistic regression with NRI	ITT Population – patients with baseline scalp involvement (PSSI baseline score >0)	Ixekizumab Q4W vs. placebo at Week 12 and all other postbaseline visits during Period 2.	Exploratory analysis
PPASI	Change from baseline	ANCOVA with LOCF; MMRM	ITT Population – patients with baseline palmoplantar involvement (PPASI baseline score >0)	Ixekizumab Q4W vs. placebo at Week 12 and all other postbaseline visits during Period 2.	Other secondary analysis
	PPASI 50 PPASI 75 PPASI 100	Fisher’s exact test with NRI Logistic regression with NRI	ITT Population – patients with baseline palmoplantar involvement (PPASI baseline score >0)	Ixekizumab Q4W vs. placebo at Week 12 and at each postbaseline visit during Period 2.	Exploratory analysis
Binary questions on psoriasis location	Proportion of patients with no psoriasis presence on face	Fisher’s exact test with NRI Logistic regression with NRI	ITT Population – patients with psoriasis presence on face at baseline	Ixekizumab Q4W vs. placebo at Week 12.	Other secondary analysis

Measure	Variable	Analysis (Method)	Population	Comparison/Time Point	Analysis Type
	Proportion of patients with no psoriasis presence on nail	Fisher’s exact test with NRI Logistic regression with NRI	ITT Population – patients with psoriasis presence on nail at baseline	Ixekizumab Q4W vs. placebo at Week 12.	
	Proportion of patients with no psoriasis presence on axilla	Fisher’s exact test with NRI Logistic regression with NRI	ITT Population – patients with psoriasis presence on axilla at baseline	Ixekizumab Q4W vs. placebo at Week 12.	
	Proportion of patients with no psoriasis presence on genital	Fisher’s exact test with NRI Logistic regression with NRI	ITT Population – patients with psoriasis presence on genital at baseline	Ixekizumab Q4W vs. placebo at Week 12.	
	Proportion of patients with no psoriasis presence on perianal region	Fisher’s exact test with NRI Logistic regression with NRI	ITT Population – patients with psoriasis presence on perianal region at baseline	Ixekizumab Q4W vs. placebo at Week 12.	

Abbreviations: ANCOVA = analysis of covariance; BSA = body surface area; ITT = intent-to-treat; LOCF = last observation carried forward; MMRM = mixed-effects model of repeated measures; NAPS I = Nail Psoriasis Severity Index; NRI = nonresponder imputation; PASI = Psoriasis Area and Severity Index; PASI 50/75/90 = at least a 50%/75%/90% improvement from baseline in PASI score; PASI 100 = a 100% improvement from baseline in PASI score; PPASI = Palmoplantar Psoriasis Area and Severity Index; PPASI 50/75 = at least a 50%/75% improvement from baseline in PPASI score; P)PASI 100 = a 100% improvement from baseline in PPASI score; PSSI = Psoriasis Scalp Severity Index; Q4W = every 4 weeks; sPGA = static Physician Global Assessment; vs. = versus.

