6.3.1. Nonresponder Imputation (NRI)

Analysis of categorical efficacy and health-outcome variables will be assessed using a NRI method. Subjects will be considered nonresponders for the NRI analysis if they do not meet the clinical response criteria or have missing clinical response data at the analysis time point. Randomized patients without at least 1 postbaseline observation will also be defined as nonresponders for the NRI analysis.

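### NAPSI = 0 (nail clearance) can be declared with up to 9 of 20 nails unscored, because the averaging rule acts before nonresponder imputation

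*SAP*

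**What the plan says.** SAP Section 6.11, Table RHCD.6.3, gives each of 20 nails a bed score (0 to 4) and a matrix score (0 to 4) and sums them to a total of 0 to 160. Missing parts are handled in three steps:

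- At nail level: "For each nail, if either bed or matrix score is missing or not done, the score for that nail is missing".
- At subject level, the condition "If <50% of the nail scores from 20 nails are missing" leads to "the imputation will be performed by using the average score of the remaining nails".
- Beyond that limit: "If ≥50% of the nail scores are missing, the NAPSI score will be left as missing".

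The responder definition is: "A NAPSI response is defined as a NAPSI score of 0, which is also referred to as nail clearance". The same table makes this response missing only when the total is missing.

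Table RHCD.6.4 analyses NAPSI = 0 by Fisher's exact test and logistic regression, both with NRI, in ITT subjects with a baseline NAPSI above 0. It labels the analysis exploratory. Section 6.3.1 defines NRI, which is applied visit by visit: "Subjects will be considered nonresponders for the NRI analysis if they do not meet the clinical response criteria or have missing clinical response data".

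In Table RHCD.6.3 the PASI, PSSI and PPASI totals are not calculated if any single component is missing.

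**The concern.** Averaging over the scored nails is a common device for a severity total. It suits an all-clear endpoint poorly. NAPSI = 0 is a statement about every nail, yet the rule lets 11 nails speak for 20. When the scored nails are all clear, each missing nail is filled with 0 and the total counts as a success. NRI is meant to stop missing data from counting as success, but it never comes into play, because by then the response is no longer missing.

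The nail-level step adds a second route. A nail with a positive bed score and no matrix score is set to missing and can then be filled with 0. Clearance could then be declared although disease is recorded on the case report form.

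What is at stake is how the nail-clearance percentage is read. No alpha, power or gated test depends on it.

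**Working it through.** **Inputs** (SAP Table RHCD.6.3): 20 nails; at most 4 + 4 = 8 points per nail; averaging when fewer than 50% of nails are missing; total missing otherwise; response = total of 0. NRI is from Section 6.3.1.

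**The plan's own range.** 20 × 8 = 160, which matches the stated maximum.

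**How many nails can be filled.** 9/20 = 45% is below 50%, and 10/20 = 50% is not. The maximum is 9.

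**Imputed total.** Let S be the sum over the scored nails and m the number missing. Then total = S + m × S/(20 − m).

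- 11 nails at 0, 9 missing: 0 + 9 × 0 = 0, a responder.
- 10 nails at 0, 10 missing: total missing, a nonresponder under NRI.
- One nail at 1, ten at 0, 9 missing: 1 + 9 × 1/11 = 1.82, a nonresponder.

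False clearance therefore needs every scored nail to be 0. In that case up to 9 × 8 = 72 of 160 points (45%) can go unobserved.

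**Direction.** Where averaging applies (m ≤ 9), a truly clear subject has S = 0 and a total of 0, so averaging never turns a cleared subject into a failure. A diseased subject can also have S = 0. The error runs one way only.

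**Recorded disease set aside.** Suppose one nail has bed = 4 and no matrix score, and the other 19 are scored 0. That nail becomes missing (m = 1), S = 0, and the total is 0: a responder.

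**Comparison with scalp clearance.** PSSI = 0 is the direct analogue. One missing PSSI component makes the score missing, the response missing, and the subject a nonresponder under NRI.

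**Illustrative size.** The documents give no missing-nail rate. Assume that m of 20 nails are missing at random and that k nails are diseased at the visit. The chance that all k are among the missing is C(20 − k, m − k)/C(20, m):

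| Diseased nails k | m = 3 | m = 5 | m = 9 |
|---|---|---|---|
| 1 | 3/20 = 15% | 5/20 = 25% | 9/20 = 45% |
| 2 | 6/380 = 1.6% | 20/380 = 5.3% | 72/380 = 18.9% |
| 3 | 6/6840 = 0.1% | 60/6840 = 0.9% | 504/6840 = 7.4% |

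With one nail missing and one diseased the chance is 1/20 = 5%. These figures hold for a subject with that pattern. They do not estimate the error in the trial's clearance rate.

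**The case against.** The best defence is that the SAP is internally consistent and the endpoint minor. NRI acts on a missing response, and Table RHCD.6.3 says when NAPSI = 0 is missing. Missed visits and 10 or more missing nails still become nonresponse. NAPSI = 0 is exploratory, outside the gated tests in Section 6.5 and outside the other-secondary list in Section 6.11.4, which names only NAPSI change. The binary question on nail psoriasis is analysed at Week 12 with NRI as an other secondary analysis. It involves no averaging, so it offers a separate check. All of this stands, and it limits the weight of the point. It does not remove the one-way error.

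A reader might infer more than the documents support:

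- *That the rule contradicts NRI.* It does not. It acts earlier and defeats the conservative intent.
- *That NAPSI is the only endpoint tolerating missing parts.* DLQI and CDLQI totals become missing only when two or more questions are missing (Table RHCD.6.5). The contrast holds for PASI, PSSI and PPASI.
- *That unexamined toenails are simply filled from fingernails.* If all ten toenails are unscored, the 50% limit applies and NRI makes the subject a nonresponder. The problem needs a partial examination, and nothing in the documents shows that toenails are skipped more often.
- *That the clearance rate is in fact inflated, or that one arm gains.* Neither can be shown without missing-nail counts by arm.
- *That the change score needs the same correction.* Unequal missingness can distort it too, but the alternatives have costs of their own. Summing only nails scored at both visits, for example, leaves the 0 to 160 scale and gives subjects different maxima.

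**Conclusion.** The point holds for NAPSI = 0 as a minor one. The component rule can declare nail clearance from 11 clear nails with 9 unscored, and can do so despite a recorded positive part-score. Where averaging applies, it can only overstate clearance relative to true status. The mechanism follows from the text and needs no assumption. The percentages rest on nails being missing at random and on few nails being diseased at the visit; selective missingness could make them larger or smaller. The net effect on the reported rate, and any difference between arms, cannot be determined from the documents.

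**What to change.** Keep the existing rule that the total is missing when 50% or more of the nails are missing. Add, for NAPSI = 0 only:

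> *NAPSI = 0 requires every nail that was scored >0 or was missing at baseline to be fully scored 0 at the visit, and no recorded bed or matrix score >0 on any nail; otherwise the response is missing and NRI applies.*

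The 50% limit must stay. Without it, a subject with one involved nail at baseline could be called cleared with 19 nails unseen. The added line still accepts up to 9 unscored nails if they were clear at baseline, so new disease there could be missed. The stricter alternative is the any-missing rule already used for PSSI = 0, which closes that gap but turns more truly clear subjects into nonresponders. Leave averaging in place for the continuous change score.

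SAP Section 3 records that Version 3 was approved after the primary database lock, and Section 6.17 places unblinding and the final Period 2 analysis at the lock that closes Period 2. The change should therefore be reported as a labelled sensitivity analysis beside the planned one, with the number of imputed nails by arm. The cost is one derivation line, some programming, a few more nonresponders and a slightly lower clearance rate.
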